## PROTOCOL SYNOPSIS

Protocol Title:	Phase 2 Open-Label Study of Safety and Efficacy Trial of CXA-10 in Pulmonary Arterial Hypertension	
Protocol Number:	STUDY19010004	
NCT Number:	NCT04125745	
Version # and Date:	Version 1.4/March 4, 2020	
Clinical Phase:	Phase II Clinical Trial	
Investigational Product:	CXA-10	
Trial Site:	Single-Center Trial	
IND Sponsor	[name] University of Pittsburgh, School of Medicine	
Principal Investigator:	[name]	
Co-Principal Investigator:	[name]	
Sub-Investigators:	[name] [name] [name] [name]	[name] [name]
Study Monitor:	[name], IND Sponsor-Investigator	
Research Facilities:	UPMC Montefiore Hospital, UPMC Presbyterian, CLC at Falk Clinic, Kaufman Medical Building	
Clinical Laboratories:	UPMC Presbyterian Hospital, Shadyside CP PUH, UPMC Clinical Laboratory Building, [name]	
Study Rationale:	To date, current therapies for pulmonary arterial hypertension (PAH) are vasodilatory and reduce the symptoms associated with pulmonary artery (PA) vasoconstriction. The ability to modify the underlying disease (re-establish the normal architecture of the pulmonary vessels and cardiac muscle and improve right ventricular (RV) function to reduce morbidity and mortality) will	

	
be the most important treatment goal for the next generation of therapies, ultimately translating to better outcomes.
 
CXA-10 has the potential to be differentiating as a “disease modifying” therapy in PAH. CXA-10 targets the oxidative stress, inflammatory and metabolic pathways shown to be important causes in this disease. Its ability to affect multiple targets is key to improving both the pulmonary vasculature and cardiac abnormalities of PAH.

Study Objectives:	
The main objective of this study is to evaluate the safety and tolerability of 12-week oral CXA-10 therapy in subjects with pulmonary arterial hypertension (PAH), with preliminary evaluation on the clinical efficacy of oral CXA-10 on changes in hemodynamics, exercise capacity, cardiovascular function and patient reported outcomes.

Study Hypothesis:	
We hypothesize that administration of CXA-10 for 12 weeks will decrease pulmonary vascular resistance (PVR) as measured by right heart catheterization (RHC), improve exercise capacity, cardiovascular function and health related quality of life in PAH patients with limited toxicity.

Study Aims:	
Aim 1: To determine the safety and tolerability of oral CXA-10 administered for 12 weeks in PAH subjects.
 
Aim 2: To characterize the efficacy of CXA-10 administered for 12 weeks in PAH subjects assessed by pulmonary vascular resistance (PVR) as measured by right heart catheterization (RHC).
 
Aim 3: To characterize the efficacy of CXA-10 administered for 12 weeks in PAH subjects on exercise capacity assessed by 6 minute walk distance and home accelerometry, cardiovascular function assessed by RHC and echocardiogram, and patient reported outcomes assessed by disease specific health related quality of life questionnaire.
 
Aim 4: To explore the pharmacokinetic-pharmacodynamic relationships of CXA-10 using sparse blood measures of drug concentrations and biomarkers associated with mechanism of action (MOA) of CXA-10 and PAH disease as endpoints in PAH subjects, if the data warrant such an analysis.

Study Design:	
This is an open-label safety study and a phase 2a pre- and post-assessment study aimed to evaluate the efficacy and safety of 12-week oral CXA-10 therapy on the changes in hemodynamics and exercise capacity in PAH patients.

	
Potential subjects will undergo a screening visit to determine that eligibility requirements are met. Subjects who meet the inclusion criteria and none of the exclusion criteria will receive oral CXA-10 at the dose of 300 mg once daily for 12 weeks.
 
The first 10 subjects enrolled will receive the first dose of the study drug in the cardiac catheterization laboratory to evaluate acute pharmacological responses during the screening RHC (Visit1). This will be repeated at the end of the 12-week study RHC (Visit 7). Hemodynamic measures such as pulmonary vascular resistance (PVR), mean pulmonary artery pressure (mPAP) and left and right ventricular filling pressures, will be measured at baseline and 30 minutes post drug dose and CXA-10 metabolites will be measured with pharmacokinetics sampling time points at baseline and 2-6 hours post drug. Food will be given prior to dosing. Subjects will have 6-minute walk distance with Borg dyspnea scale assessments. Plasma NT-proBNP level, the World Health Organization (WHO) Functional Class assessment, and a health related quality of life questionnaire will also be collected. To evaluate in vivo insulin action in stimulating glucose disposal, oxidation, and nonoxidative disposal. An intravenous glucose tolerance test (IVGTT) will be performed before and after 12 weeks of CXA-10 treatment.
 
Subjects will be evaluated at 4-week intervals for occurrences of adverse events, laboratory test abnormalities, and evaluations of NT-proBNP plasma levels, six-minute walk distance with Borg dyspnea scale assessments, WHO functional classification and health related quality of life questionnaire recorded. Additional blood samples will be obtained for biomarkers and cytokines analysis, and physical activities will be monitored using a noninvasive accelerometer before and after study drug treatment.

Planned Sample Size:	27 completed subjects
Duration of Treatment:	12 weeks
Major Inclusion Criteria:	
 
• Male or female between 18-80 years of age inclusive at screening
 
• Weight <math>\geq</math> 40 kg or 88 lbs.
 
• Have a WHO Classification of Functional Status Class II or III
 
• Must meet all of the following hemodynamic criteria by means of a right heart catheterization: mPAP of <math>\geq</math>25 mmHg, PVR <math>\geq</math>
 

	
3 wood units, PAWP of <math>\leq</math>15 mmHg. A clinical RHC done within 2 months may be acceptable to determine eligibility.
 
 
• Meet all of the following pulmonary function test parameters, completed no more than 12 months before Screening or at screening: forced expiratory volume in one second (FEV1) <math>\geq</math> 60% of predicted normal and forced vital capacity (FVC) <math>\geq</math> 60%
 
• A 6 MWD test of <math>\geq</math> 100 m and <math>\leq</math> 600 m at Screening
 
• Participants enrolled in an exercise program for pulmonary rehabilitation must be in a stable program 1 month prior to Screening and must agree to maintain their current level of rehabilitation throughout the study. If subjects are not enrolled in an exercise training program for pulmonary rehabilitation they cannot enroll during the screening/baseline period or throughout the study
 
• If receiving HMG-CoA reductase inhibitors (i.e., statins) subjects must not have changed their dose <math><</math>4 weeks prior to Screening
 
• If receiving simvastatin-containing products: simvastatin (Zocor), Vytorin, or any other combination therapy containing simvastatin, the subject's simvastatin dose should not exceed 20 mg/day. Note: Subjects using a simvastatin product at dose <math>></math> 20 mg/day may be rescreened if their dose has been adjusted to <math>\leq</math> 20 mg/day, at least 4 weeks prior to Screening with no dose or regimen changes within 4 weeks prior to Baseline
 
• Subjects must be receiving one or more of the following previously approved PAH therapies: phosphodiesterase type 5 inhibitors (PDE5), endothelin receptor antagonist (ERA), soluble guanylate cyclase (sGC) stimulator, prostanooids, prostacyclin receptor agonists and must be on stable doses (<math>\geq</math> 3 months) with no dose adjustment within 1 month of Screening
 
• Ability to provide written informed consent
 

Major Exclusion Criteria:	
 
• Portopulmonary hypertension and pulmonary veno-occlusive diseases
 
• Congenital heart defects (i.e., atrial septal defects, ventricular septal defects, and patent ductus arteriosus) repaired less than 1 year prior to Screening (Group 1 classification of Pulmonary Hypertension)
 
• Systolic blood pressure <math>></math> 160 or <math><</math> 90 mmHg or diastolic blood pressure <math>></math> 110 mmHg at Screening
 
• QTcF interval of <math>></math>500 msec on triplicate supine ECGs Screening (Visit 1)
 
• Acute myocardial infarction or acute coronary syndrome (ST-Elevation Myocardial Infarction (STEMI), Non STEMI
 

	
(NSTEMI) and/or unstable angina) within the last 90 days prior to Screening
 

Recent cerebrovascular accident/transient ischemic attack (CVA/TIA) within the last 90 days prior to Screening

Recent hospitalization for left heart failure within the last 90 days prior to Screening

Clinically significant aortic or mitral valve disease defined as greater than moderate regurgitation or moderate stenosis; pericardial constriction; restrictive or constrictive cardiomyopathy; left ventricular dysfunction (LVEF < 50%); left ventricular outflow obstruction; symptomatic coronary artery disease; autonomic hypotension; or fluid depletion in the opinion of the investigator

Evidence of a life-threatening cardiac arrhythmias on ECG at Screening as determined by the physician investigator

Personal or family history of congenital prolonged QTc syndrome or sudden unexpected death due to a cardiac reason

Receiving intravenous inotropes (e.g. dopamine, dobutamine) within 2 weeks prior to Screening

History of angina pectoris or other condition that was treated with long or short acting nitrates <12 weeks of Screening

History of herbal or natural medication use (including fish oil) within 2 weeks or 5 half-lives, whichever is longer, prior to Baseline

Subject has taken prednisone at doses > 15 mg/day; if immunosuppressive medications are used the dose must be stable within 12 weeks prior to Screening and throughout the study

The subject is currently taking a drug that may affect the assay measurement of serum creatinine (e.g. cimetidine, Bactrim, Pyridium)

Newly prescribed drug or increased dose of an existing drug that is known to prolong the QTc interval and has been associated with Torsades de Pointes Note: Stable doses of these drugs are permitted (i.e., subject has received the same dose and regimen for at least 30 days prior to Screening with no anticipated changes to the dose or regimen during the course of the study)

--	---

	
 
• The subject is currently taking dimethyl fumarate (Tecfidera™)
 
• Females with a positive urine pregnancy test at Screening or prior to dosing or who are pregnant or breastfeeding or who are trying to conceive.
 
• Recent (within 6 months) history of abusing alcohol or illicit drugs
 
• History of any primary malignancy, including a history of melanoma or suspicious undiagnosed skin lesions, with the exception of basal cell or squamous cell carcinomas of the skin or cervical carcinoma in situ or other malignancies curatively treated and with no evidence of disease for at least 5 years or prostate cancer who is not currently or expected, during the study, to undergo radiation therapy, chemotherapy, and/or surgical intervention, or to initiate hormonal treatment
 
• Cardiovascular, liver, renal, hematologic, gastrointestinal, immunologic, endocrine, metabolic, central nervous system or psychiatric disease that, in the opinion of the investigator, may adversely affect the safety of the subject and/or efficacy of the investigational product or severely limit the lifespan of the subject other than the condition being studied
 
• Clinically significant hyperthyroidism or hypothyroidism not adequately treated
 
• Any other condition and/or situation that causes the Investigator to deem a subject unsuitable for the study (e.g., due to expected study medication non-compliance, inability to medically tolerate the study procedures, or a subject's unwillingness to comply with study-related procedures)
 
• The subject has known hypersensitivity to the CXA-10, the metabolites, or formulation excipients
 
• The subject has had treatment with any investigational drug within 30 days or 5 half-lives (whichever is longer) prior to Screening or plans to participate in an investigational drug study at any time during this study
 

Study Endpoints:	
Primary Endpoint: The primary endpoint measures the incidences of treatment-emergent adverse events.
 
Secondary Endpoints:

	
The primary efficacy endpoint measures the change from baseline in Pulmonary Vascular Resistance (PVR) assessed by Right Heart Catheterization at 12 weeks.
 
Other secondary endpoints measure:
 

• Change from baseline in hemodynamic parameters including Cardiac Output (CO), Cardiac index (CI), mean Pulmonary Artery Pressure (mPAP), Pulmonary Artery Wedge Pressure (PAWP), Mean Right Atrial Pressure (mRAP), and compliance (SV/ (sPAP-dPAP) at 12 weeks

• Change from baseline in RV function including tricuspid annular plane systolic excursion (TAPSE) and tissue Doppler of the lateral tricuspid valve anulus (S') as assessed by echocardiograms at 12 weeks

• Change from baseline in functional exercise capacity by assessing 6 minute walk distance test with Modified Borg Dyspnea Scale at 12 weeks

• Change from baseline in the levels of serum NT-proBNP at 12 weeks

• Change from baseline in WHO Functional Class at 12 weeks

• Change from baseline in patient reported outcomes measured by PAH-SYMPACT® questionnaire at 12 weeks

• Change from baseline in daily physical activity assessed by personalized activity monitor at 12 weeks

• Pharmacokinetic endpoint: CXA-10 parent and metabolites

 
Exploratory Endpoints:
 

• Change in insulin sensitivity by intravenous glucose tolerance test at 12 weeks

• Pharmacodynamic endpoint: change from baseline in serum biomarkers, leptin, inflammatory cytokines (IL-17, IL-6, TNF<math>\alpha</math>, MCP-1) and hsCRP at 12 weeks

• Pharmacokinetic - Pharmacodynamic relationship of CXA-10 on relevant efficacy, safety and biomarkers endpoints

• Epidemiological relationships of oral and gut microbiome and PAH

--	--

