### **Visit 1 (Screening)**

Screening assessment will be performed within about 4 weeks prior to baseline testing (Visit 2) and will take place on two (2) separate days if a screening right heart catheterization (RHC) is needed. Subjects will be asked to fast a minimum of 8 hours prior to each visit.

- Obtain written informed consent.
- Review Inclusion and Exclusion criteria
- Medical history review and demographics
- Complete physical exam
- Weight, height
- Electrocardiogram (ECG)
- Vital signs (temperature, respiratory rate, blood pressure, heart rate) and pulse oximetry
- Clinical lab testing and urinalysis (fasting glucose, comprehensive metabolic panel, fasting lipid profile, complete blood count, platelet and differential [CBC/Diff/Plt], uric acid, PT/INR and hemoglobin A1C).
- RHC. This will be completed if not done within the prior 2 months to verify eligibility or may be repeated at study PI discretion. For a RHC to be considered eligible within 2 months, the subject must be stable on their medications and should not have started a new exercise program right before the prior cath or since the RHC within 2 months leading up to screening or baseline. Pulse oximetry and automated blood pressures will be measured at regular intervals.
- Hemodynamic measures such as pulmonary vascular resistance (PVR), mean pulmonary artery pressure (mPAP) and left and right ventricular filling pressures, will be measured at baseline and 30 minutes post drug dose and CXA 10 metabolites will be measured with pharmacokinetics sampling time points at baseline and 2-4 hours post drug dose. Food will be given prior to dosing. Research blood samples for biomarkers, cytokines measurements (samples collected at the same times as PK samples)
- NT Pro-BNP
- Urine pregnancy test in women of childbearing potential (i.e. women who are not at least 1 year post-menopausal or who have not undergone a surgical sterilization procedure)
- Pulmonary function testing (PFT) must have been completed, no more than 12 months prior to the start of screening visit. If this has not been performed, a new PFT will be obtained.
- 6 minute walk test (6MWT) with Borg Dyspnea Scale
- Oral (saliva, tongue scraping) and stool samples for microbiome analysis; subjects may be provided a stool collection kit and return the sample in a pre-paid envelope by USPS mail.
- WHO Functional Class assessment
- Concomitant medications assessment
- AE assessment

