### **Efficacy Assessments**

Right Heart Catheterization (RHC): RHC is performed routinely as a clinical standard of care procedure for diagnostic purposes in this population. RHC will be performed at Screening and at the end of the treatment (Visit 6 – Week 12).

Briefly, RHC will be performed with a balloon tipped, flow-directed, pulmonary artery catheter (e.g. 7F Swan Ganz catheter) inserted through a sheath in the internal jugular vein under continuous

ECG monitoring. An alternate vein may be used at the physician's discretion. All measurements will be recorded with the subject in a supine position, at rest, breathing room air or with supplementary oxygen to obtain peripheral saturations above 90%. Hemodynamic recording of right atrial, right ventricular, pulmonary artery pressures, pulmonary artery wedge pressure and cardiac output will be made. Parameters for analysis will include: Mean RAP, RVSP, RVDP, PASP, PADP, Mean PAP, Mean PAWP, Thermodilution Cardiac Output, PVR, Cardiac Index, and Pulmonary Vascular Compliance. Mixed venous oxygen saturation (SvO2) will be determined from a sample drawn from the Swan-Ganz catheter. Other parameters may be obtained as data permit.

**Echocardiogram:** Noninvasive transthoracic echocardiograms will be completed to assess RV function by measures such as tricuspid annular plane systolic excursion (TAPSE) as well as tissue Doppler of the lateral tricuspid valve anulus (S').

**Six Minute Walk Distance Test and Borg Dyspnea Scale:** The 6MWD test will be performed according to a protocol-specific modification of the American Thoracic Society guidelines. The 6MWD test measures the distance an individual is able to walk over a total of six minutes on a hard, flat surface. The Borg Scale is a method of rating perceived exertion during exercise. It should be performed immediately after the 6MWD test.

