## **2.4 STUDY ENDPOINTS**

Primary Endpoint:

The primary endpoint measures the incidences of treatment-emergent adverse events.

Secondary Endpoints:

The primary efficacy endpoint measures the change from baseline in Pulmonary Vascular Resistance (PVR) assessed by Right Heart Catheterization at 12 weeks.

Other secondary endpoints measure:

- Change from baseline in hemodynamic parameters including Cardiac Output (CO), Cardiac index (CI), mean Pulmonary Artery Pressure (mPAP), Pulmonary Artery Wedge Pressure (PAWP), Mean Right Atrial Pressure (mRAP), and compliance (SV/ (sPAP-dPAP) at 12 weeks
- Change from baseline in RV function including tricuspid annular plane systolic excursion (TAPSE) and tissue Doppler of the lateral tricuspid valve anulus (S') as assessed by echocardiograms at 12 weeks
- Change from baseline in functional exercise capacity by assessing 6 minute walk distance test with Modified Borg Dyspnea Scale at 12 weeks
- Change from baseline in the levels of serum NT-proBNP at 12 weeks
- Change from baseline in WHO Functional Class at 12 weeks
- Change from baseline in patient reported outcomes measured by PAH-SYMPACT® questionnaire at 12 weeks
- Change from baseline in daily physical activity assessed by personalized activity monitor at 12 weeks
- Pharmacokinetic endpoint: CXA-10 parent and metabolites

Exploratory Endpoints:

- Change in insulin sensitivity by intravenous glucose tolerance test at 12 weeks
- Pharmacodynamic endpoint: change from baseline in serum biomarkers, leptin, inflammatory cytokines (IL-17, IL-6, TNF $\alpha$ , MCP-1) and hsCRP at 12 weeks
- Pharmacokinetic - Pharmacodynamic relationship of CXA-10 on relevant efficacy, safety and biomarkers endpoints, if the data allow
- Epidemiological relationships of oral and gut microbiome and PAH

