## 2.5.2 Statistical Analysis

Change of each outcome from baseline will be presented by median (IQR). Primary analysis will be performed by paired t-test comparing continuous outcome in 12-weeks vs. baseline. All data will be tested for normality, and non-normal data will be tested by Wilcoxon signed rank test. We will also use mixed effect models with restricted maximum likelihood estimation to test the change of outcome during the 12 weeks of intervention.

Demographics and baseline characteristics will be listed and summarized descriptively. Safety will be evaluated via the incidence of AE's, changes in clinical labs, and vital signs. AEs will be coded by system organ class and preferred term according to the most recent edition CTCAE. AEs will be summarized by frequency, severity, and relationship to study medication. Clinical labs will be compared to normal ranges and flagged if found to be of clinical concern. Results will be presented as observed changes and depicting changes from baseline to defined study timepoints.

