## **3.2 INCLUSION CRITERIA**

The following criteria will be required on ALL subjects:

- Male or female between 18-80 years of age inclusive at Screening
- Weight  $\geq$  40 kg or 88 lbs
- Have a WHO Classification of Functional Status Class II or III
- Must meet all of the following hemodynamic criteria by means of a right heart catheterization: mPAP of  $\geq$ 25 mmHg, PVR  $\geq$  3 wood units, PAWP of  $\leq$ 15 mmHg. A clinical RHC done within 2 months is acceptable to determine eligibility
- Meet all of the following pulmonary function test parameters, completed no more than 12 months before Screening or at screening: forced expiratory volume in one second (FEV1)  $\geq$  60% of predicted normal and forced vital capacity (FVC)  $\geq$  60%
- A 6 MWD test of  $\geq$  100 m and  $\leq$  600 m at Screening
- Participants enrolled in an exercise program for pulmonary rehabilitation must be in a stable program 1 month prior to Screening and must agree to maintain their current level of rehabilitation throughout the study. If subjects are not enrolled in an exercise training program for pulmonary rehabilitation they cannot enroll during the Screening/Baseline Period or throughout the study
- If receiving 3-hydroxy-3-methyl-glutaryl-coenzyme A (HMG-CoA) reductase inhibitors (i.e., statins) subjects must not have changed their dose  $<$ 4 weeks prior to Screening
- If receiving simvastatin-containing products: simvastatin (Zocor), Vytorin, or any other combination therapy containing simvastatin, the subject's simvastatin dose should not exceed 20 mg/day  
Note: Subjects using a simvastatin product at dose  $>$  20 mg/day may be rescreened if their dose has been adjusted to  $\leq$  20 mg/day, at least 4 weeks prior to Screening with no dose or regimen changes within 4 weeks prior to Baseline
- Subjects must be receiving one or more of the following previously approved PAH therapies: phosphodiesterase type 5 inhibitors (PDE5), endothelin receptor antagonist (ERA), soluble guanylate cyclase (sGC) stimulator, prostanooids, prostacyclin receptor agonists and must be on stable doses ( $\geq$  3 months) with no dose adjustment within 1 month of Screening
- Ability to provide written informed consent

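### The RHC that admits a subject is by default also the baseline, so the one-arm test of PAWP change is biased toward a rise; any PVR bias is small and of uncertain size

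*Combined protocol and SAP*

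**What the plan says.** The Synopsis and section 3.2 set three entry limits on an RHC. Subjects "Must meet all of the following hemodynamic criteria by means of a right heart catheterization", among them PVR of at least "3 wood units, PAWP of" at most 15 mmHg. Section 3.2 adds: "A clinical RHC done within 2 months is acceptable to determine eligibility". On the screening RHC, Visit 1 says: "This will be completed if not done within the prior 2 months to verify eligibility or may be repeated at study PI discretion".

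Under Efficacy Assessments, "RHC will be performed at Screening and at the end of the treatment". Visits 2 and 3 contain no RHC, and Appendix A shows none between Screening and the end of treatment.

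On endpoints, "The primary efficacy endpoint measures the change from baseline in Pulmonary Vascular Resistance (PVR) assessed by Right Heart Catheterization at 12 weeks". Section 2.4 lists change in PAWP, mPAP and CO among the other secondary endpoints. Section 2.1 describes a one-arm study. Section 2.5.2 says: "Primary analysis will be performed by paired t-test comparing continuous outcome in 12-weeks vs. baseline", with a Wilcoxon signed rank test for non-normal data.

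No section states which RHC is the baseline when a subject has more than one, and section 2.5 does not mention selection on the baseline value.

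**The concern.** An upper limit on PAWP, applied to the reading later used as baseline, admits some subjects whose wedge pressure was low by chance on that day. On a second measurement their average moves back up without treatment. A control arm would show the same drift and cancel it. Here the change is tested against zero, so the drift counts as change on treatment. The Wilcoxon test has the same weakness.

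The lower limits on PVR and mPAP act the other way on those quantities. In addition, PVR = (mPAP − PAWP)/CO, so a wedge rise by itself lowers calculated PVR. A fall in PVR is the favourable direction and is the efficacy result the study seeks. At stake are the PAWP test, and how a modest PVR fall is read if PAWP has risen at the same time.

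**Working it through.** **The plan's own figure.** Section 2.5.1 assumes a PVR decrease of 2.3 WU with SD 4.1. The standardised effect is 2.3/4.1 = 0.561. A two-sided 5% paired t-test needs n = 26.9, so 27, with power 0.801. The sample size is correct and is not in question.

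**PAWP by formula.** With an upper cut-off c, true mean μ, between-subject SD σ_b and within-subject SD σ_w, the expected rise on remeasurement is (σ_w²/σ_T) × φ(a)/Φ(a), where σ_T = √(σ_b² + σ_w²) and a = (c − μ)/σ_T. The documents give only c = 15. Assume μ = 10.5, σ_b = 3, and σ_w of 2 or 3 mmHg.
- σ_w = 2: σ_T = 3.61, a = 1.25, rise = (4/3.61) × 0.183/0.894 = 0.23 mmHg.
- σ_w = 3: σ_T = 4.24, a = 1.06, rise = (9/4.24) × 0.227/0.856 = 0.56 mmHg.

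This uses the PAWP cut-off alone. When mPAP and PAWP errors are independent, the PVR cut-off also favours low wedge readings and adds a little.

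**All three cut-offs together, zero drug effect, n = 27.** Further assumptions, none from the documents: true PVR lognormal with median 5, 7 or 9 WU and log-SD 0.5; CO 4.5 (SD 0.9) L/min; between-catheterization SD of 3 mmHg for mPAP and 10% for CO. The nominal rate in one direction is 2.5%. The two columns differ only in how wedge error relates to mPAP error.

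| Quantity | Errors independent | Wedge error passes 1:1 into mPAP |
|---|---|---|
| Mean PAWP change (mmHg) | +0.25 to +0.71 | +0.12 to +0.50 |
| Significant PAWP rise | 6.5 to 14% | 4 to 9% |
| Mean PVR change (WU) | −0.08 to −0.27 | 0.00 to −0.07 |
| Significant PVR fall | 3.9 to 12.7% | 2.3 to 4.7% |
| Mean change in mPAP/CO (WU) | −0.03 to −0.12 | −0.05 to +0.11 |

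**PVR against the plan.** 0.27/2.3 = 12%, and 0.08/2.3 is about 4%. The high PVR rates occur where the simulated SD of change is about 1.7 WU. At the plan's 4.1 WU the largest drift is 0.27/(4.1/√27) = 0.27/0.789 = 0.34 standard errors. That gives a fall in about 5% of null trials and a two-sided rate of about 6.3%.

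**Stress cases.**
- Allowing one haemodynamic re-screen (end of section 3.3), with independent errors: PAWP +0.29 to +0.79 mmHg, PVR −0.10 to −0.32 WU.
- Four other populations, from typical mPAP 50 down to 32 mmHg with larger errors, independent: PAWP +0.19 to +1.30 mmHg, PVR −0.06 to −0.64 WU. With mPAP and PAWP errors correlated 0.7: PAWP +0.17 to +0.67 mmHg, PVR 0.00 to −0.23 WU.
- Baseline taken from an RHC separate from the qualifying one: both drifts are zero to the precision of the simulation.

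**The case against.** The strongest objection is that the documents contain no test-retest data, so every size here is assumed. For PVR even the presence of a drift depends on an assumption. Wedge pressure is the downstream pressure for mPAP, so a session-to-session wedge change should move mPAP too, and the two then largely cancel in the gradient. This stands. A reader might infer that all three cut-offs necessarily push PVR down and that the PVR test exceeds its 5% level. The documents do not support that: the drift is close to nil when wedge error passes into mPAP, and small at the plan's SD of 4.1.

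Second, no section defines the qualifying RHC as the baseline. A discretionary repeat is allowed. The first 10 subjects also have a pre-dose reading at the RHC where they are dosed, and any of them who qualified on an earlier clinical RHC would have a separate baseline. This stands as a limit on how many subjects are affected. It does not remove the problem, because the default schedule has one pre-treatment RHC and no rule for choosing between two.

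Third, PVR is a secondary endpoint in a study whose primary endpoint is adverse events, and changes in mPAP, PAWP and CO are already listed as endpoints. This lowers the severity. Listing the components separately still does not show how much of the PVR change each one carries.

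A reader might also think that mPAP/CO avoids the difficulty because it has no wedge term. It does not. It comes from the same reading, selected on mPAP of at least 25, and in most of the settings where wedge error passes into mPAP it drifts upward.

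**Conclusion.** The concern holds for PAWP. By default its baseline is truncated at 15 mmHg, and the paired test against zero is biased toward a rise: about +0.1 to +0.7 mmHg with no drug effect, and a significant rise in roughly 4 to 14% of null trials instead of 2.5%. The size rests on the assumed variances. The direction was the same in every setting run.

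For PVR the finding is weaker. A downward drift of 0.00 to 0.27 WU is possible, at most about 12% of the planned 2.3 WU under the main assumptions, and its size depends on how far mPAP and PAWP errors move together. A population lying closer to the cut-offs, with larger measurement errors, could show more. No simulated setting came near 2.3 WU, so a reader should not infer that selection alone could produce the planned effect. The practical risk is a modest PVR fall accompanied by a PAWP rise. Severity is low to moderate.

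**What to change.** Amend section 2.5.2 before the data are examined:

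1. Report PAWP change descriptively with a confidence interval and no p-value, giving truncation of the baseline at 15 mmHg as the reason.
2. Beside the PVR change, report the contributions of mPAP, PAWP and CO with 95% confidence intervals. An exact split per subject, writing G = mPAP − PAWP and c = 1/CO, is ΔPVR = ΔmPAP × c̄ − ΔPAWP × c̄ + Δc × Ḡ, where bars denote the mean of the two visits.
3. State that a PVR fall arising mainly from a PAWP rise cannot be separated from selection on the baseline reading.
4. Define the baseline RHC. Where a subject has a pre-dose RHC separate from the qualifying one, use that later reading, provided eligibility is not judged again on it. Report how many subjects have one.
5. Show mPAP/CO, if at all, as supportive only, noting that it is also selected and can be biased in either direction.

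Mean PAP, mean PAWP and thermodilution CO are already recorded at each RHC, so no procedure, visit or subject is added. The cost is some plan wording, one extra table, and the loss of the formal PAWP test.
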